6.4.3.3. Additional Estimates

For the subgroup analyses by Candida species, only descriptive statistics will be provided; no statistical testing will be performed due to possible small sample size.

All other efficacy data will be summarized, but not subject to formal statistical analysis.

6.5 Treatment Cycle 2

A second treatment cycle will be allowed for subjects who did not achieve sufficient clinical improvement (e.g. VSS remains ≥ 3) on the randomized treatment (Cycle 1) as evaluated at the TOC and FU visits. A second treatment cycle will also be allowed for subjects with clinical cure/improvement/success who experience a recurrence before the last FU visit. During Cycle 2, subjects may receive additional treatment with ibrexafungerp for a period up to 14 days as recommended by the investigator and following discussion with the sponsor.

6.5.1. Efficacy Analysis (Treatment Cycle 2)

The proportion of Cycle 2 subjects enrolled in MITT, ITT and PP populations will be summarized in each table.

Secondary, and exploratory efficacy analysis will be analyzed the same as for cycle 1.

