14.10. Vulvovaginal Samples for KOH and Fungal Culture

At Screening, a vulvovaginal specimen will be obtained for direct microscopic examination with 10% KOH. Subjects must have a positive KOH test at screening to be enrolled. The screening KOH will be assessed at the site by the investigator or qualified designee. A vaginal sample will also be obtained at screening, at the TOC and at the first FU visit at 14 days after EOT for fungal culture and species identification by the central laboratory and for susceptibility testing against ibrexafungerp and additional antifungal agents (per CLSI M27-A3 guidelines). If there is persistence or recurrence of vulvovaginal symptoms, additional vulvovaginal specimens will be collected for KOH testing at the TOC and at the FU visits, and for fungal culture at the FU visits. Samples will also be obtained at any unscheduled visit, if needed.

If the subject experiences persistence or worsening or recurrence of symptoms that per the investigator's assessment (e.g. symptoms ≥ 4) warrant the use of rescue antifungal therapy, the subject may be enrolled into Treatment Cycle 2 and receive additional treatment with ibrexafungerp for a period up to 14 days as recommended by the investigator and following discussion with the sponsor.

Whether or not a subject enters Treatment Cycle 2, or be prescribed rescue therapy, a vaginal examination with collection of samples for KOH (assess at the site) and culture should be completed prior to initiation of Treatment Cycle 2 or rescue therapy. If the KOH test is negative, the investigator should consider other causes for the persistence or worsening of the symptoms and antifungal rescue medication may not be indicated. If the collection of the vaginal culture is not possible prior to the initiation of the rescue therapy, it should still be collected as soon as possible after rescue therapy is given.

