18.2. Analysis Populations

The study populations to be used in the analyses are defined as follows:

Intent-to-Treat (ITT) Population: All ibrexafungerp-treated subjects.

Modified Intent-to-Treat (MITT) Population: All treated subjects who have a positive culture for *Candida species* at Screening.

Per-Protocol (PP) Population: All MITT subjects who have completed the study drug treatment, who did not have major protocol deviations likely to affect study efficacy AND who have a TOC evaluation.

Safety Population: All enrolled subjects who received at least one dose of study drug.

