4.2.2. Secondary Endpoints

Efficacy as measured by:

- The percentage of subjects with clinical improvement:
 - Total composite score of 2 on the VSS scale at the TOC and FU visits
 - Total composite score of 1 on the VSS scale at the TOC and FU visits.
- The percentage of subjects with total composite score equal or less than 2 and equal or less than 1 on the VSS scale at the TOC and FU visits.
- The percentage of subjects with clinical success (at least 50% reduction from baseline in the total composite VSS score) with no additional antifungal therapy required based on investigator's judgment) at the TOC and FU visits.
- The percentage of subjects with mycological response (defined as a negative culture for growth of *Candida spp.* or subject is asymptomatic, therefore culture not done) at the TOC and FU visits.
- The percentage of subjects with both clinical cure and mycological response at the TOC and FU visits.
- The percentage of subjects with clinical cure at the FU visits.
- The absolute change in total composite VSS score from baseline to the TOC and FU visits.

Exploratory Endpoints:

- Absolute improvement in QOL outcomes at TOC and FU visits compared to baseline as measured by QOL survey.
- Subjects whose signs and symptoms have resolved enough that additional antifungal treatment was not required based on clinical judgement.
- Time to resolution of symptoms.

Safety and Tolerability as measured by:

Adverse events (AEs), vital signs, treatment discontinuation, and safety laboratory tests.

5. Study Design

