6.1.1. Baseline and Change from Baseline Definition

Baseline is defined as the last assessment prior to the first dose of study drug. If time and date are available, then the baseline assessment could be on the same day as first dose so long as it's before the time of first dose. If time is not available, the date prior to first dose will need to be used. Change from baseline is defined as: non-missing post- baseline value – baseline value. Baseline values will be re-calculated in Cycle 2 for QOL scale, VVS composite score, physical examinations, lab results and vital signs. If above baseline value is not available in Cycle 2, then use the last available value in Cycle 1 as baseline for Cycle 2.

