6.2. Analysis Populations

The study populations to be used in the analyses are defined as follows:

Intent-to-Treat (ITT) Population: All ibrexafungerp-treated subjects.

Modified Intent-to-Treat (MITT) Population: All treated subjects who have a positive culture for *Candida* species at Screening.

Per-Protocol (PP) Population: All MITT subjects who have completed the study drug treatment, who did not have major protocol deviations likely to affect study efficacy AND who have a TOC evaluation.

Safety Population: All enrolled subjects who received at least one dose of study drug.

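### Cycle 2 mycological response is analysed in a set fixed by the pre-Cycle 1 Screening culture, so subjects already culture-negative at re-entry can count as Cycle 2 responders

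*SAP*

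**What the plan says.** SAP 6.2 defines MITT as "All treated subjects who have a positive culture for *Candida* species at Screening", and Protocol 18.2 agrees. PP is a subset of MITT. Neither document gives a Cycle 2 version of either set.

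SAP 6.5.1 uses these populations for Cycle 2 ("The proportion of Cycle 2 subjects enrolled in MITT, ITT and PP populations will be summarized in each table") and adds: "Secondary, and exploratory efficacy analysis will be analyzed the same as for cycle 1". Mycological response, assessed at TOC and at follow-up, is among those secondary endpoints. SAP 4.2.2 lists it as "The percentage of subjects with mycological response (defined as a negative culture for growth of *Candida spp.* or subject is asymptomatic, therefore culture not done". The combination of clinical cure and mycological response is listed too. Both depend on status at the visit; neither asks for a positive culture at the start of the cycle.

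Under SAP 6.5 a subject may enter Cycle 2 because clinical improvement was insufficient (the example is a VSS score still at 3 or more) or because of a recurrence after a clinical response. No culture result is a condition. Protocol section 15 starts the Cycle 2 schedule at the Baseline visit, so Screening is not repeated.

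Two provisions bear on the state at re-entry. SAP 6.1.1 says: "Baseline values will be re-calculated in Cycle 2 for QOL scale, VVS composite score, physical examinations, lab results and vital signs". Culture is not named. Protocol 14.10 says that "collection of samples for KOH (assess at the site) and culture should be completed prior to initiation of Treatment Cycle 2", and asks the investigator to think of other causes if the KOH test is negative.

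**The concern.** Requiring a positive Candida culture for the primary efficacy set is the sponsor's own principle: a rate of clearing an organism is informative only in subjects who have the organism when treatment starts. In Cycle 1 the Screening culture serves that purpose. In Cycle 2 the same culture is out of date. It predates a full course of treatment, and some subjects may have cleared Candida while keeping signs or symptoms that qualify them for retreatment.

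A reader will probably take the Cycle 2 mycological rate as the effect of a further course on persistent or recurrent Candida infection. As planned, it mixes that effect with a condition that some subjects already met on entry.

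**Working it through.** The plan has no figure to reproduce. It gives no sample size calculation, no expected number entering Cycle 2 and no expected Cycle 2 rate. The check is therefore a trace of the definitions, followed by an illustration on assumed values.

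**Trace, two hypothetical subjects**

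1. Culture positive at Screening, so in MITT. At TOC the culture is negative but VSS is 3, so she may enter Cycle 2. Nothing in SAP 6.2 or 6.5.1 removes her from MITT. Her culture is still negative at the Cycle 2 TOC visit, so she is a Cycle 2 mycological responder.
2. Enrolled on a positive KOH test, but her central Screening culture is negative, so she is outside MITT. She later has a recurrence with a positive culture and is retreated. She stays outside MITT, although she is a subject in whom eradication by Cycle 2 could be observed.

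**Size for mycological response**

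Take the Screening-based MITT subjects who enter Cycle 2. All three inputs are assumptions:

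- f: share culture-negative at re-entry
- s: probability that these subjects count as responders at the Cycle 2 visit (still negative, or asymptomatic with no culture taken)
- e: eradication rate among those culture-positive at re-entry

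Reported rate = f × s + (1 − f) × e.

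Inflation over e = f × s + (1 − f) × e − e = f × (s − e).

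Reported rate, with inflation in percentage points:

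| e | s | f = 0 | f = 10% | f = 30% | f = 50% |
|---|---|---|---|---|---|
| 50% | 1.0 | 50% (0) | 55% (+5) | 65% (+15) | 75% (+25) |
| 30% | 1.0 | 30% (0) | 37% (+7) | 51% (+21) | 65% (+35) |
| 70% | 1.0 | 70% (0) | 73% (+3) | 79% (+9) | 85% (+15) |
| 50% | 0.9 | 50% (0) | 54% (+4) | 62% (+12) | 70% (+20) |

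For example, with e = 50%, s = 1 and f = 30%: 0.30 × 1 + 0.70 × 0.50 = 0.65, and 0.30 × (1 − 0.50) = 0.15.

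**In counts (assumed)**

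Suppose 30 MITT subjects enter Cycle 2. Nine are culture-negative at re-entry and stay so, and 10 of the other 21 clear.

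- As planned: (9 + 10)/30 = 19/30 = 63.3%, Clopper-Pearson 95% CI 43.9% to 80.1%.
- Restricted to those positive at re-entry: 10/21 = 47.6%, 95% CI 25.7% to 70.2%.

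Two limits apply. The restricted set would also admit subjects like the second one above, so its rate equals e only if they clear at the same rate. And the formula sizes mycological response alone. The combined endpoint uses the same denominator and the same mycological component, but it also needs clinical cure, so these figures do not carry over to it.

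**The case against.** **Weight.** The study is exploratory and not powered for comparisons. SAP 6.4.2.2 plans only frequencies and percentages for mycological response. Cycle 2 is uncontrolled, with a duration that the investigator recommends. No test or stated decision rests on this rate. All of that stands and limits the importance of the point. It does not justify the denominator: a descriptive rate is still read.

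**Safeguards.** Protocol 14.10 calls for KOH and culture before Cycle 2 and tells the investigator to look for other causes if KOH is negative, and Cycle 2 follows discussion with the sponsor. This may well keep f low, possibly near zero. But it is advice, not an entry condition, KOH is not culture, and no population uses the pre-Cycle 2 culture.

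**Reading of the SAP.** Laboratory results are on the re-baselining list in 6.1.1 and might be taken to include culture. SAP 6.6.2 suggests that hematology and chemistry were meant. On either reading a baseline value would be reset, not MITT membership. That Cycle 2 MITT uses the Screening culture is inferred from there being only one definition; the mock tables are a separate document and might say more.

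**Interpretability.** As planned, the rate does have a meaning: the share of Screening-positive, retreated subjects who meet the response definition after Cycle 2. It is not a rate of eradication by Cycle 2.

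**Stronger readings to resist.** A reader might infer that Cycle 2 clinical cure is pulled down because culture-negative symptoms are not candidal. The documents have no data on cure in such subjects. They do report cure without active drug (28.6% and 44.0% on placebo in the two earlier Phase 3 trials), so no direction can be asserted. A reader might also take study SCY-078-306 as a guide to f: 449 subjects were treated and 272 were in its mITT set, so 177/449 = 39.4% fell outside. That was before treatment and in acute VVC; it is no estimate of the share culture-negative at re-entry.

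**Conclusion.** The point holds for Cycle 2 mycological response and for clinical cure plus mycological response, in MITT and in PP. The written rules allow a subject who is already culture-negative at re-entry to count as a responder, and they leave out a subject who was negative at Screening but positive before Cycle 2.

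The size cannot be derived from the documents. On assumed values it runs from nothing (f = 0), through +5 points (f = 10%), to +25 points (f = 50%), with s = 1 and e = 50%. It is smaller if eradication is higher or if some negative entrants turn positive again. An inflation of any particular size is therefore not established; only the mechanism is.

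The effect is confined to descriptive Cycle 2 results. The Cycle 1 primary endpoint is unaffected, and nothing is concluded about Cycle 2 clinical cure on its own. The change is worth making before database lock because the cost is small and the rate is otherwise easy to misread.

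**What to change.** In the SAP:

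1. **6.5.1:** add a Cycle 2 mycologically evaluable set (Cycle 2 MITT): subjects treated in Cycle 2 whose last Candida culture before the first Cycle 2 dose is positive. Use the pre-Cycle 2 sample under Protocol 14.10 or, if there is none, the culture from the TOC or follow-up visit at which Cycle 2 was decided.
2. **6.1.1:** add culture result and species to the items re-baselined for Cycle 2.
3. **Main set:** use this set for Cycle 2 mycological response and for clinical cure plus mycological response.
4. **Other entrants:** report the numbers culture-negative at re-entry and with no culture at re-entry as two separate categories. A missing culture is then neither assumed positive nor merged with the negatives.
5. **Sensitivity analysis:** keep the Screening-based MITT, so that the effect of the choice can be seen.

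This is SAP wording and programming only. Treatment, Cycle 2 entry and sampling do not change. The pre-Cycle 2 culture is something that should be taken rather than a strict requirement, so some will be missing. The cultures scheduled at TOC and at 14 days after end of treatment, and those taken for symptoms at later follow-up visits, provide the fallback. The price is a smaller set, wider intervals and probably a lower reported Cycle 2 mycological rate.

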6.6. Safety Analyses

6.6.1. Adverse Events

A Treatment-emergent adverse event (TEAE) is defined as any AE that occurs on or after the start time of the study drug administration. AEs will be coded using the MedDRA 26.0 dictionary.

A summary of TEAEs will be presented as the number and percentage of subjects with at least one of the following:

- Any AE
- Any TEAE

- Treatment-related TEAE
- Serious TEAE
- Treatment-related serious TEAE
- TEAE leading to study drug withdrawal
- TEAE leading to death

TEAEs will be summarized by SOC and preferred term for each treatment group. For subjects with the same SOC and preferred term occurring more than once, the first occurrence will be tabulated. TEAEs will also be presented for each preferred term by maximum severity, by highest relationship to study drug, and for serious AEs. In the overall summary, additionally, the number and percentage of patients with at least one severe TEAE, with at least one moderate TEAE but no severe TEAE and with only mild TEAEs will be provided.

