| Abbreviation | Definition |
|--------------|------------------------------|
| AE | Adverse event |
| ATC | Anatomical Therapeutic Class |

| Abbreviation | Definition |
|--------------|--|
| BID | Twice a Day |
| BMI | Body Mass Index |
| CRF | Case report form |
| EOT | End of therapy |
| FU | Follow Up |
| HIV | Human immunodeficiency virus |
| ITT | Intent-to-Treat |
| MedDRA | Medical Dictionary for Regulatory Activities |
| MITT | Modified Intent-to-Treat |
| PP | Per-Protocol |
| PT | Preferred term |
| QOL | Quality of Life |
| SAP | Statistical analysis plan |
| SAE | Serious adverse event |
| SD | Standard deviation |
| SOC | System organ class |
| TEAE | Treatment-emergent adverse event |
| TFLs | Tables, figures, and listings |
| TOC | Test of Cure |
| VVC | Complicated Vulvovaginal Candidiasis |
| VSS | Vulvovaginal Signs and Symptoms Scale |
| WHODrug | World Health Organization Drug Enhanced Dictionary |

3. Introduction

The purpose of this statistical analysis plan (SAP) is to describe the procedures and statistical methodologies that will be used in the analysis and reporting of results for SCYNEXIS, Inc. Protocol SCY-078-307b.

This document is prepared based on the following documents:

- the study protocol version 3.0 dated 17 January 2022.
- the case report form (CRF) version 1.2 dated 9 September 2022.

Readers are referred to the final study protocol, the CRF, and CRF completion guidelines for details of the study design, conduct and data collection. This SAP must be finalized prior to the locking of the clinical database for this study. The mock tables, figures, and patient data listings (TFLs) are provided in a separate document.

4. Objectives and Endpoints

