6.3. Demographics and Study Summary

6.3.1. Patient Disposition

The number of subjects enrolled, number completing the study, and reasons for discontinuation will be summarized by treatment group and by cycle.

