6.3.6. Study Drug Administration

Treatment Cycle 1: All randomized subjects

Subjects who meet all the inclusion and none of the exclusion criteria will be randomized to treatment and stratified into 2 groups based on the Candida species and presence or absence of underlying conditions. Subjects will receive open-label oral ibrexafungerp 300 mg BID for one, three or seven consecutive days per [TABLE 1](#):

| Treatment Group | Criteria | Ibrexafungerp Dose Randomization and Stratification |
|-----------------|---|---|
| Group A | Subjects without underlying medical conditions AND known to have isolates other than C glabrata, C krusei, C auris | 1 Day dosing (300mg AM and 300mg PM) N = 50 |
| Group B | Subjects with underlying medical conditions: DM, immunocompromised conditions (e.g. HIV), debilitation, immunosuppressive therapy (e.g. corticosteroids), recurrent VVC (≥ 3 episodes/year) AND/OR known to have C glabrata, C krusei or C auris isolates | 3 Days or 7 Days dosing (300mg AM and 300mg PM) Randomized 1:1 N = 50:50 |

6.4. Efficacy Analyses Cycle 1

The efficacy analyses will be conducted using the MITT (primary analysis population), ITT and PP populations to evaluate ibrexafungerp. Efficacy outcomes will be presented by treatment group in Cycle 1.

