6.4.1.2. Main Analysis Approach

Clopper-Pearson method will be used to summarize 95% CI of proportion of clinical cure for group A and group B separately. Pairwise treatment comparison of subjects in group B 3 days vs. subjects in group B 7 days will be performed to test primary efficacy endpoint (clinical cure at TOC visit) using a Fisher's Exact

test; p-values and 95% confidence intervals for odds ratio will be presented. The primary endpoint will also be analyzed of subjects in group B 3 days vs. subjects in group B 7 days using a Cochran-Mantel-Haenszel row mean scores test stratified by site.

VSS scores at Baseline, TOC, and FU will be summarized for each sign and symptom using frequency counts and percentages.

Summary statistics will be provided for the total VSS composite score (observed value and change from baseline). Student's t-test will be used for pairwise treatment comparison of subjects in group B 3 days vs. subjects in group B 7 days; p-values and 95% confidence intervals will be presented for the differences between treatment groups.

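### SAP 6.6.1 gives TEAEs no end date and no cycle split, so as written Cycle 2 events fall in the Cycle 1 regimen columns; SAP 6.5.1 also carries the Group B 3 vs 7 day log-rank into Cycle 2

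*SAP*

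**What the plan says.** **Adverse events.** SAP 6.6.1 counts as treatment-emergent "any AE that occurs on or after the start time of the study drug administration". It then states that "TEAEs will be summarized by SOC and preferred term for each treatment group". A term that recurs in the same subject is tabulated once, at its first occurrence, and "TEAEs will also be presented for each preferred term by maximum severity, by highest relationship to study drug, and for serious AEs". Nothing in SAP 6.6 mentions cycle or closes the window.

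**Treatment groups.** The SAP defines these only by Cycle 1 regimen: Group A (1 day) and Group B (3 or 7 days, randomised 1:1) in the SAP 6.3.6 table. SAP 6.4.1.2 also calls the two Group B arms treatment groups: "p-values and 95% confidence intervals will be presented for the differences between treatment groups".

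**Cycle 2.** SAP 6.5 allows a second course of up to 14 days after insufficient improvement or recurrence. The investigator recommends its length after discussion with the sponsor.

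**Where the SAP does separate cycles.**
- Disposition (6.3.1): "reasons for discontinuation will be summarized by treatment group and by cycle".
- Baselines (6.1.1): "Baseline values will be re-calculated in Cycle 2 for QOL scale, VVS composite score, physical examinations, lab results and vital signs".
- Efficacy (6.4): "Efficacy outcomes will be presented by treatment group in Cycle 1".
- Time to resolution (6.4.3.1): collected in each cycle separately.
- Cycle 2 efficacy (6.5.1): secondary and exploratory analyses follow the Cycle 1 methods.

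The exploratory methods in SAP 6.4.3.2 include a log-rank test of Group B 3 days against 7 days.

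**The concern.** The TEAE table by treatment group is the planned safety description of the 1-, 3- and 7-day regimens. If Cycle 2 events enter it, each column mixes the labelled regimen with a later course that was not randomised and may be longer. A 14-day course is 14, 4.7 and 2 times the Cycle 1 length of the three regimens (14/1, 14/3, 14/7). The first-occurrence, maximum-severity and relationship rules have no cycle limit either, so a severe Cycle 2 event would displace a mild Cycle 1 event of the same term. No planned TEAE summary would show how re-treatment was tolerated.

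The Cycle 2 log-rank raises a separate problem. Its subjects are selected on Cycle 1 outcome and receive individually chosen durations. A p-value labelled 3 vs 7 days would therefore be neither a randomised comparison nor a comparison of Cycle 2 durations.

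**Working it through.** **Text check.** A subject randomised to Group B 3 days enters Cycle 2 and has a first event of nausea on the fifth day of that course. The event occurs after study drug started, so 6.6.1 makes it a TEAE. Her only defined treatment group comes from Cycle 1, so it is tabulated there. No sentence in SAP 6.6 redirects it.

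For the log-rank, 6.4.3.1 supplies Cycle 2 time-to-resolution data, 6.4.3.2 names the test, and 6.5.1 repeats exploratory analyses in Cycle 2. Together they carry the test over. The Fisher, Cochran-Mantel-Haenszel and t-tests stand under the primary analysis (6.4.1.2), which 6.5.1 does not carry over.

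**Inputs.** The plan gives no figure for this point. The TEAE rates cited in Protocol 7.1.4 for the 1-day regimen recompute: 99/298 = 33.2% and 150/247 = 60.7%. The treatment-related rate in the first of these trials is 14.8%. Allocation is 50 per regimen. The documents give no re-treatment share f. Non-cure in the same two trials was 100 - 63.3 = 36.7% and 100 - 50.5 = 49.5%. This is only a loose guide: those trials enrolled acute VVC, residual scores of 1-2 would not meet the example Cycle 2 threshold of VSS 3 or more, and recurrences would add entrants. I assume f = 20-40%.

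**Points added to any-TEAE by pooling,** with Cycle 1 risk p1, Cycle 2 risk p2 and independence: (1 - p1) × f × p2.

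| Scenario | f = 20% | f = 40% |
|---|---|---|
| p1 = p2 = 0.332 | 0.668 × 0.2 × 0.332 = 4.4 | 8.9 |
| p1 = p2 = 0.607 | 0.393 × 0.2 × 0.607 = 4.8 | 9.5 |
| p1 = 0.332, p2 = 0.148 (related only) | 0.668 × 0.2 × 0.148 = 2.0 | 4.0 |
| p1 = 0.607, p2 = 0.148 (related only) | 0.393 × 0.2 × 0.148 = 1.2 | 2.3 |

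In the first two rows this is about 2-5 subjects per 50. With a within-subject correlation of 0.5 between cycles, the equal-risk figures halve to 2.2-4.8 points.

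**Spurious Group B difference,** with equal true Cycle 1 risk and re-treatment of 20% in one arm and 40% in the other (assumed): 0.2 × (1 - p) × p = 4.4 points (p = 0.332) or 4.8 points (p = 0.607).

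**Sampling noise for that difference at 50 per arm:** 1.96 × sqrt(2p(1 - p)/50) = 18.5 points (p = 0.332) or 19.1 points (p = 0.607).

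**Cycle 2 denominators:** 50 × f = 10-20 entrants per arm.

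**The case against.** **Pooling is inferred.** No sentence says that Cycle 2 events go into the Cycle 1 columns, and "The mock tables, figures, and patient data listings (TFLs) are provided in a separate document". The Cycle 2 baselines for laboratory results and vital signs suggest that by-cycle safety output may be intended. This stands as a limit: a reader might infer that the sponsor has decided to pool, and the documents do not show that. They show that 6.6.1, followed as written, pools.

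**Fewer Cycle 2 events may be recorded.** Protocol 14.19 and 16.9 restrict new events after TOC to related events, vaginal infections and events leading to certain treatments, and Cycle 2 starts at or after the Cycle 1 TOC. Protocol 15 restarts the visit schedule in Cycle 2, so full capture is plausible, but the text does not say which cycle's TOC applies. This stands, and the related-only rows approximate it.

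**Some added events are background.** Placebo TEAE rates in the cited trials were 50.8% and 29.1%. Part of the addition therefore reflects longer observation rather than Cycle 2 drug effect.

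**SAP 6.4.3.3 says all other efficacy data get no formal analysis.** That sentence sits in the Cycle 1 section and covers what is not otherwise specified. It does not cancel a log-rank test named in 6.4.3.2 and repeated through 6.5.1.

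**The split can be produced at reporting.** Onset relative to dosing is to be determined for each event (Protocol 16.9) and every subject has a profile (SAP 6.7). This is true, and it keeps the cost low, but the rule should be fixed before lock.

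**Conclusion.** The concern holds on the SAP text. TEAEs have no end date or cycle split, and an exploratory log-rank test is carried into a population where it is not a randomised comparison.

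The size rests on an assumed 20-40% re-treated and on 1-day rates from acute VVC trials: 4.4-9.5 points on any-TEAE with equal, independent risk per cycle, about 1.2-4.0 if only related events are captured in Cycle 2, and less again with within-subject correlation.

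Two stronger conclusions are tempting and not supported. One is that the 3 vs 7 day safety picture is materially distorted. That needs Group B columns split by duration and different re-treatment in the two arms. Even then the 4-5 points are about a quarter of the roughly 19-point sampling half-width, and no formal safety test is planned. The other is that the efficacy conclusion is at risk. The primary endpoint is clinical cure at TOC, analysed in Cycle 1, and is unaffected.

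Severity: minor to should-fix.

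**What to change.** **SAP 6.6.1.** Add TEAE tables by cycle.
- Cycle 1 runs from the first Cycle 1 dose to before the first Cycle 2 dose, in columns A 1-day, B 3-day and B 7-day.
- Cycle 2 runs from the first Cycle 2 dose, with Cycle 2 entrants as denominator and first occurrence applied within cycle. List the duration received rather than cross-tabulating it, because the numbers are small.
- Keep the whole-study table by assigned regimen as a labelled supplement. It is a legitimate summary.

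**SAP 6.1.2.** Add a rule assigning partially dated events to a cycle. At present a missing day can be set to the first of the month, and a missing start to the first dose, either of which can place a Cycle 2 event before the first Cycle 2 dose.

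**SAP 6.5.1.** State that Cycle 2 efficacy is descriptive only, with no 3 vs 7 day log-rank.

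**Minor.** The sponsor should clarify which cycle's TOC ends full adverse event recording (Protocol 14.19 and 16.9, read with Protocol 15).

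**Cost.** SAP wording and one extra set of tables with small Cycle 2 denominators. The split needs no new data, and the last item needs a protocol clarification.
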